9.2 Screening/Baseline Evaluation

Patients will be prescreened for eligibility and if qualified will be approached with the study information and asked if they are willing to participate. The Screening visit will occur within 30 days prior to the procedure.

Informed consent will be obtained per Section 13.3. All patients who sign a consent form are considered study subjects. A study participant is considered enrolled after they have signed an informed consent form and after the inclusion/exclusion criteria have been met.

The following evaluations are required at the time of subject screening /baseline:

- Demographic Information: gender, race, age, weight, and height, and smoking status.
- Medical / Surgical History.
- Pre-operative blood draw for determination of coagulation disorders if warranted.

LVT009 Revision: B Date: 19 Jun 24	CONFIDENTIAL	Page 17 of 39	
This document contains proprietary and confidential information of Levita Magnetics.			
Do not copy, dis tribute, or share with others without prior written authorization from Levita Magnetics.			

• Urine pregnancy test for women of childbearing potential. Note that if the screening test is more than 1 week prior to the index procedure, a second urine pregnancy test is required within 7 days of the index procedure.

9.3 Procedure

The Investigator will perform the surgical procedure in accordance with the methods detailed in the Instructions for Use.

The following intra-operative data will be collected:

- General anesthesia time.
- Operative time (from the first incision to the last suture's placement).
- Device and procedure observations.
- Conversion to open surgical procedure.
- The need for an additional surgical tool to mobilize the liver.
- Estimated blood loss.
- Video recording of the overall procedure.
- Adverse events.
- Device malfunctions.

9.4 **Post-Procedure / Hospital Discharge**

Before hospital discharge the following data will be collected:

- Length of hospital stay (time from admittance to post-anesthesia care unit until hospital discharge).
- Length of time spent in Post Anesthesia Care Unit (PACU).
- Adverse events, if any.

9.5 Follow-up

All subjects will be asked to return to the investigational site at 7 days and again at 30 days post-procedure according to the study schedule described in **¡Error! N o se encuentra el origen de la referencia..** Subjects will be queried about adverse events at these study visits. Study visits should be scheduled as closely as possible to the earlier part of the visit window to allow for rescheduling if needed due to last minute schedule changes. Visits not completed within the specified time period will be regarded as deviations.

9.6 Unplanned Follow-up Visits

Subjects returning for unscheduled visits will be reported on the Unscheduled Visit case report form.

LVT009 Revision: B Date: 19 Jun 24	CONFIDENTIAL	Page 18 of 39

9.7 Early Discontinuation / Withdrawal

All subjects will be informed of their right to withdraw from the clinical study at any time without penalty or loss of benefits to which the subject is otherwise entitled. Additionally, the Investigator may prematurely discontinue any subject's participation in the study if the Investigator feels that the subject can no longer fully comply with the requirements of the study or if any of the study procedures are deemed potentially harmful to the subject. The reason for early discontinuation will be documented in the source documents and the Study Termination case report form.

9.8 Lost to Follow-up Subjects

Every attempt will be made to have all subjects complete the follow-up visit schedule. A subject will not be considered lost to follow-up unless efforts to obtain compliance are unsuccessful. At a minimum, the effort to obtain follow-up information will include three attempts to make contact via telephone or email and if unsuccessful, then a certified letter from the Investigator will be sent to the subject's last known address. In general, the study site coordinator should attempt to contact the subject after each missed visit to reschedule the visit.

9.9 Study Exit

Subjects will be considered to have completed and exited the study after the 30 day follow up visit has been completed.

9.10 Study Schedule of Assessments

	Time Frame			
Assessment	Pre-op	Index Procedure	7 day follow-up	30 day follow- up
Visit Window	- 30 days	NA	(± 3 days)	(± 7 days)
Informed Consent	\checkmark			
Medical History	\checkmark			
Demographics	\checkmark			
Blood Tests	\checkmark			
Pregnancy Test *	\checkmark			
Intra-operative assessments		\checkmark		

Table 1: Schedule of Assessments

CONFIDENTIAL

Page 19 of 39

Adverse events				
----------------	--	--	--	--

* Urine pregnancy test for all women of childbearing potential at pre-op visit and repeated within 7 days of index procedure unless pre-op visit/prior urine pregnancy test was within 7 days of index procedure.

10. RISK / BENEFIT ANALYSIS

10.1 Benefits

Possible benefits of the Levita Magnetic Surgical System are a reduction in the number of surgical incisions needed to perform the surgery, with associated reduction in post-operative pain and scaring, a shorter length of stay in the hospital, and a faster recovery.

10.2 Risks

There are risks associated with use of the Levita Magnetic Surgical System including:

- Electromagnetic field incompatibility or interference.
- Malfunctioning of the device.
- Breakage of the device.
- Allergic reaction related to the device.
- Abdominal wall/cavity/tissue and/or organ injury or damage (e.g. inflammation, redness).
- Infection.
- Tissue damage, including hematoma, bleeding or petechiae.
- Vascular injury.
- Gastro-intestinal injury.
- Organ perforation.
- Need for extended surgery.
- Additional surgical intervention due to any of the above factors (includes reoperation).

These adverse events do not include all adverse events, which occur with surgery in general, but are important considerations particular to laparoscopic instrumentation.

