The Magnetic Grasper Device is actuated via its handle with two distinct scissortype motions to open and close the Detachable Grasper jaws and to release the Detachable Grasper from the Delivery/Retrieval Shaft. The Magnetic Grasper Device can be used for mobilization in the same manner as a conventional tissue grasper, or its Detachable Grasper can be released and used with the external Magnetic Controller. When the Detachable Grasper is released from the Delivery/Retrieval Shaft, the Delivery/Retrieval Shaft can be removed and mobilization of the tissue can be achieved through the magnetic attraction between the Detachable Grasper and the external MC. This access port is therefore available for use with other surgical tools. When the procedure is completed, the Delivery/Retrieval Shaft may be reinserted to retrieve the Detachable Grasper.

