5. INDICATION FOR USE

The Magnetic Surgical System is designed for grasping the liver and the tissue surrounding the crus of the diaphragm and retract the liver in bariatric and/or hiatal hernia procedures to facilitate access to and visualization of the surgical site (**Figure 3**).

LVT009 Revision: B Date: 19 Jun 24	CONFIDENTIAL	Page 14 of 39
This document contains proprietary and confidential information of Levita Magnetics.		
Do not copy, dis tribute, or share with others without prior written authorization from Levita Magnetics.		

[figure not shown]

Figure 3. Intended Use

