14. ADVERSE EVENTS

14.1 Definitions

14.1.1 Adverse Event (AE)

AEs are any untoward medical occurrence, unintended disease or injury, or untoward clinical signs (including abnormal laboratory findings) in

LVT009 Revision: B Date: 19 Jun 24	CONFIDENTIAL	Page 26 of 39
This document contains propriatory and confidential information of Lovita Magnetic		Lovita Magnotias

which subjects, users or other persons, whether or not related to the investigational medical device. This definition includes events related to the procedures involved. For users or other persons, this definition is restricted to events related to investigational medical devices.

All adverse events, regardless of relationship to the device, must be recorded on the case report forms provided. Adverse events that occur during this study should be treated by established standards of care.

Adverse events shall be assessed by the Investigator as to its relationship and level of relatedness to the investigational device, assessment, and/or procedure, and documented at the time of the procedure and at all study follow-up visits.

Each Investigator shall provide source documentation as requested by the Sponsor to facilitate reporting and adjudication of these events.

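### Grasp-site tissue damage is a listed device risk, but no standardised check is recorded at grasper retrieval, so symptom-free local injury may be under-recorded

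*Combined protocol and SAP*

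**What the plan says.** **The risk.** Section 10.2 names "Tissue damage, including hematoma, bleeding or petechiae" as a risk of the system. Section 5 describes the use as "grasping the liver and the tissue surrounding the crus of the diaphragm" to retract the liver. Section 3.1 presents the longer tip, and its use on crural tissue, as what is new in Version 2.

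**The safety outcome.** Under 7.1 and 11.3, safety is adverse events, summarised by relatedness, seriousness and severity. There is no separate outcome for local tissue injury.

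**At the operation.** The intra-operative list in 9.3 includes adverse events, "Device and procedure observations", "Estimated blood loss" and "Video recording of the overall procedure". Section 14.1.1 requires the investigator to assess adverse events, "documented at the time of the procedure and at all study follow-up visits". Section 4 says that when the procedure is completed "the Delivery/Retrieval Shaft may be reinserted to retrieve the Detachable Grasper". It mentions no inspection or recording step at that moment.

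**Afterwards.** For days 7 and 30, section 9.5 says "Subjects will be queried about adverse events at these study visits". Section 10.3 adds that the visit is with an investigator, who evaluates the subject for device-related events. Table 1 lists blood tests before surgery only, and lists no examination or imaging.

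**The concern.** Injury to the tissue that the jaws hold is the harm most specific to a grasping device, and here both the tip and one attachment site are new. Feasibility has a dedicated intra-operative item, the need for another tool to mobilise the liver. Local tissue injury has none. It reaches the database only if someone judges a finding to be an adverse event and opens a form for it.

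That route is weakest for lesions that cause no symptoms. A subject cannot report petechiae or a small hematoma on the liver or crus, and an outpatient visit without imaging is unlikely to show them. If they are missed, a low device-related count would be read as evidence of local safety when it is only a lower bound. This matters because 11.2 expects 30 subjects to provide appropriate evidence of safe use, 12.4 allows the results to support a regulatory submission, and 11.7 plans a look after 15 subjects.

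**Working it through.** **1. Can the general adverse event system capture a silent grasp-site lesion?**

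| Step | What the protocol provides | What it leaves open |
|---|---|---|
| Definition (14.1.1) | Injury and clinical signs count, so a visible lesion can qualify without symptoms | Whether minor marks at the grasp site are meant to count |
| Detection at retrieval (4, 9.3) | General observations, adverse events, blood loss, video | No stated grasp-site look, lesion type or grade; no reader or criteria for the video; blood loss covers the whole procedure |
| Severity (14.3) | Mild, moderate, severe, life-threatening | The mildest grade depends on the subject noticing the event, so a lesion seen only by the surgeon has no natural grade |
| Recording (14.2) | An event must be reported on the adverse event form | With no event there is no form, so absence covers both inspected without injury and not inspected |
| Completeness (12.1) | Every CRF field must be filled, with a code for not done | The rule acts only on fields that exist; the protocol names none for the grasp site |
| Missing data (11.6) | Only subjects with non-missing safety data are used | Cannot be applied to this risk unless inspection status is known |
| Days 7 and 30 (9.5, 10.3) | Query, and evaluation by an investigator | Content of the evaluation not stated |

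Capture is therefore possible, and reporting of a recognised event is mandatory. What is missing is a solicited observation with a known denominator.

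**2. How much could this matter?**

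The plan has no figure to reproduce. Section 11.2 gives 30 subjects with no event rate, precision target, alpha or power. What follows is an illustration. The input from the documents is n = 30. The true injury rate p and the share s of injuries recorded are assumptions.

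Zero recorded injuries, one-sided 95% upper bound on the true rate: (1 − 0.05^(1/30)) / s = 0.0950 / s.

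Probability that at least one injury is recorded: 1 − (1 − p·s)^30.

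| Share recorded, s | Upper bound if none recorded | P(at least one recorded), p = 5% | P(at least one recorded), p = 10% |
|---|---|---|---|
| 1.00 | 9.5% | 78.5% | 95.8% |
| 0.75 | 12.7% | 68.2% | 90.4% |
| 0.50 | 19.0% | 53.2% | 78.5% |
| 0.25 | 38.0% | 31.4% | 53.2% |

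At the interim look, n = 15 gives 1 − 0.05^(1/15) = 18.1% with full recording, and 0.181 / 0.50 = 36.2% if half are recorded.

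The table shows only that a zero count cannot be interpreted without knowing s. It does not estimate s.

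**The case against.** The protocol is far from silent. Intra-operative adverse events, observations, blood loss and whole-procedure video are all collected. Recording adverse events is a duty under 14.1.1 and 14.2, and 10.2 names the very lesions at issue, so trained surgeons are alerted to them. An investigator evaluates subjects at follow-up. The CRFs may already contain a grasp-site field, and the Instructions for Use, to which 9.3 defers for method, may call for inspection. The study is descriptive, and the lesions most likely to be missed are the least consequential on the list.

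Much of this stands, and it rules out several stronger readings:

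- *That nothing is assessed at release.* 9.3 and 14.1.1 show otherwise. What is absent is a specific or standardised assessment.
- *That follow-up rests only on asking the subject.* 10.3 adds an investigator's evaluation, although it names no examination.
- *That such damage can be seen only at release.* No section says so. Bleeding may show earlier or later. The point is strongest for petechiae and small hematomas.
- *That injury is being under-recorded.* Without a detection rate, the CRFs or the Instructions for Use, the text supports only that it may be.

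Three things remain. An inspection instruction would not by itself put a result on the CRF. Source verification (12.2) cannot recover a lesion that nobody wrote down. Video with no reader or criteria is material for an assessment, not an assessment.

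**Conclusion.** The point holds as a gap in ascertainment. For a listed, device-specific risk, the protocol relies on event-triggered reporting where a solicited item would give a known denominator. Symptom-free injury to the liver or crural tissue may be under-recorded, and a low or zero count would not be clear evidence of local safety.

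The size is unknown. The upper bounds of 9.5% to 38.0% for zero recorded events in 30 rest on assumed recording shares from 1.00 to 0.25, on recording that is equally likely for every injury, and on no false reports. The finding also assumes that the unseen CRFs hold no grasp-site field. If they do, the remaining task is to name it in 9.3 and tabulate it in 11.4. This is a worthwhile, inexpensive improvement. It does not invalidate the design and implies no change in sample size.

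**What to change.** Add to 9.3, and to the index-procedure column of Table 1, one forced-choice CRF item completed at grasper retrieval for each tissue grasped: none / petechiae / hematoma / bleeding / laceration or perforation / not inspected. Show the site on the video that is already required.

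In 11.4, report the count in each category, including not inspected, over all subjects in whom the device was used, beside the adverse events. State how many subjects had each tissue grasped. Because the table is by type of finding, it does not depend on the severity scale in 14.3. Findings that meet the adverse event definition are still reported as adverse events.

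The cost is one CRF line per tissue, filled in while the camera is still in place, with no extra visit, test or staff. The 12.1 rule on completing every field then applies to it. The downside is that more minor findings will be reported. The change concerns data capture only and leaves clinical management as it is.

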10.3 Minimization of Risk and Monitoring Procedures

Levita Magnetics has attempted to mitigate risks as much as possible through product design and development which included *in vivo* performance testing, human factors testing, non-clinical performance testing, biocompatibility testing, sterilization validation, reprocessing validation and shelf-life validation. Additionally, careful labeling, instructions for use (IFU) and training are provided as detailed below.

LVT009 Revision: B Date: 19 Jun 24	CONFIDENTIAL	Page 20 of 39

Risks will be further mitigated through selection of qualified physicians with competence in minimally invasive surgery, appropriate training, and study monitoring.

Investigators who participate in the study will be experienced and skilled in laparoscopic surgical techniques. Additionally, Investigators, in conjunction with the investigational site, will have adequate resources for participation in a clinical study.

The study has been designed to ensure treatment and follow-up of subjects consistent with current medical practice.

Each Investigator will ensure oversight and approval of the study by the Ethics Committee (EC) prior to initiation of the clinical study at his/her investigational site.

The Investigator and study personnel will be trained on the clinical protocol. All Investigators who have not previously used the Levita MSS will undergo training with simulation models using the MSS prior to first use during the clinical study.

All Investigators and operating room support personnel will be provided with a detailed IFU during training and as a reference for review as needed.

The IFU details appropriate safety zones for use of the Magnetic Controller in an OR setting and considerations for users of a product with a strong magnet.

Study personnel are also trained with and receive a "Magnetic Surgery Screening Checklist" and Operating Room (OR) signage to ensure safe use of the system for subjects and users.

Subjects will be carefully evaluated against the inclusion/exclusion criteria prior to entering the clinical study to ensure that their diagnosis and medical status are appropriate for participation in the clinical study.

Subjects will be monitored up to the 30-day follow-up visit as defined in the study protocol. The follow-up visit will be with an Investigator to monitor the subjects' status.

A study Investigator will evaluate the subject for any adverse events potentially related to the device.

Levita Magnetics or its designee will conduct monitoring visits at the investigative sites at the initiation of the study and periodically throughout the study to evaluate protocol compliance and to determine if there are any issues that may affect the safety or welfare of the subjects.

LVT009 Revision: B Date: 19 Jun 24	CONFIDENTIAL	Page 21 of 39
This document contains p	roprietary and confidential information of	Levita Magnetics.

11. STATISTICAL SECTION

11.1 Statistical Methods

Data collected in the study will be presented using various descriptive statistics. Descriptive summaries will be the basis of study reports to generate an overall summary of the safety and effectiveness for the device.

Descriptive tables will be produced for baseline characteristics including demographics and medical history.

Missing data on study endpoints will be described.

11.2 Sample Size Justification

This is a single-arm, multicenter investigational study and considering the pivotal trial that supported the first marketing authorization in the United States for use of the device in cholecystectomy procedures, enrollment of 30 subjects is expected to provide appropriate evidence of safe and effective use of MSS in this additional subject population.

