7.2 Feasibility Outcomes

Ability to adequately mobilize the liver to achieve an effective exposure of the target tissue. Adequate mobilization is not achieved if it is necessary to use another liver retractor during the procedure.

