11.4 Safety

All adverse events for participants in the safety population will be reported. See **Section 14** for definitions

- Serious Adverse Events.
- Non-serious Adverse Events.
- Device Related Serious Adverse Events.

Results will include the number of participants experiencing each type of event as well as the number of events.

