11.6 Handling Missing Data

Only subjects with non-missing data for safety will be used.

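### Section 11.2 presents 30 subjects as adequate evidence of safety and effectiveness but states no rate or precision, and section 11 plans no confidence interval

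*Combined protocol and SAP*

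**What the plan says.** Section 11.2 states that "enrollment of 30 subjects is expected to provide appropriate evidence of safe and effective use of MSS in this additional subject population". The basis offered is "the pivotal trial that supported the first marketing authorization in the United States for use of the device in cholecystectomy procedures". No success rate, event rate, sample size or precision is carried over from that trial, and none is stated for this one. The Synopsis and section 8.2 make 30 a ceiling.

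On analysis, section 11.1 says: "Descriptive summaries will be the basis of study reports to generate an overall summary of the safety and effectiveness for the device". Section 11.4 says: "Results will include the number of participants experiencing each type of event as well as the number of events". The only list of statistics in section 11 is in 11.5 and concerns demographics: mean, median, SD, range and frequencies. No interval is named anywhere in the document.

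The effectiveness measure is a yes/no outcome defined in 7.2: "Adequate mobilization is not achieved if it is necessary to use another liver retractor during the procedure". Section 11 has no subsection on how it will be analysed.

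On who is counted, sections 7 and 8.2 refer to subjects in whom the system is used. Section 11.4 says "All adverse events for participants in the safety population will be reported", but the supplied text does not define that population. Section 11.6 adds: "Only subjects with non-missing data for safety will be used". Section 11.1 also says: "Missing data on study endpoints will be described".

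**The concern.** Section 11.2 asserts in advance that the evidence will be adequate, without saying what 30 subjects can show. Section 12.4 allows the results to support a regulatory submission. A table with no serious device-related events, or with every retraction successful, could then be read as establishing safety and effectiveness, although 30 subjects cannot exclude event rates of around one in ten. The risks listed in 10.2 include vascular injury and organ perforation, for which rates well below that would matter.

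The safety denominator adds to the problem. If subjects with incomplete safety data are removed, a person in whom the device was used can disappear from the proportion meant to describe its safety. In a study of this size, one subject visibly moves the limits.

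**Working it through.** **Can the 30 be reproduced?** No. The documents give no confidence level, power, expected rate, performance goal, target interval width or dropout allowance, so no sample-size formula has inputs. What can be computed is the precision that the stated size delivers.

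**Inputs.** n = 30 comes from 11.2 and is a maximum in the Synopsis and 8.2. The 95% level is an assumption, with 90% and 99% shown as a range. The smaller sizes (25 and 20) and the true event rates (2% and 5%) are also assumptions, for illustration.

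**Formulas (Clopper-Pearson, two-sided level 1 − α).** With 0 events in n, the upper limit is 1 − (α/2)^(1/n). With n successes in n, the lower limit is (α/2)^(1/n). For other counts x, the lower limit is the α/2 quantile of Beta(x, n − x + 1) and the upper limit is the 1 − α/2 quantile of Beta(x + 1, n − x).

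**Results at n = 30.** At 95%, 0.025^(1/30) = 0.8843, so the zero-event upper limit is 1 − 0.8843 = 0.1157.

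| Result in 30 subjects | 90% | 95% | 99% |
|---|---|---|---|
| 0 events, upper limit | 9.5% | 11.6% | 16.2% |
| 1 event, upper limit | 14.9% | 17.2% | 22.3% |
| 30/30 successes, lower limit | 90.5% | 88.4% | 83.8% |
| 29/30 successes, lower limit | 85.1% | 82.8% | 77.7% |

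For 28/30 successes the lower 95% limit is 77.9%.

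**Results if fewer are enrolled (95%).** 0.025^(1/25) = 0.8628 and 0.025^(1/20) = 0.8316.

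| n | 0 events, upper limit | All successes, lower limit |
|---|---|---|
| 30 | 11.6% | 88.4% |
| 25 | 13.7% | 86.3% |
| 20 | 16.8% | 83.2% |

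**Chance of seeing no event at all in 30.** At a true rate of 2%, 0.98^30 = 0.5455, or 55%. At 5%, 0.95^30 = 0.2146, or 21%.

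**Who is counted.**
- *Safety.* Sections 7 and 8.2 would keep everyone in whom the system is used. Section 11.6 may then remove some of them, and the population in 11.4 is undefined. As an illustration, one event in 30 has an upper limit of 17.2%. If that subject were dropped for incomplete safety data, 0 events in 29 would give 1 − 0.025^(1/29) = 1 − 0.8806 = 11.9%.
- *Feasibility.* Section 9.3 records the need for an additional liver-mobilizing tool during the operation, and 11.6 concerns safety data only. Loss to follow-up therefore does not remove a feasibility result.
- *Attempted use.* Section 9.1.2 excludes subjects whose target-tissue abnormality is found after surgery has started and prevents use of the device. Section 7.2 counts needing another retractor as failure. A subject in whom the device was tried, set aside because of anatomy and replaced by another retractor fits both rules. With 29 other successes, exclusion gives 29/29, lower limit 0.025^(1/29) = 88.1%; failure gives 29/30, lower limit 82.8%.

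**The case against.** The strongest reply is that this is a small, open-label, single-arm study titled as one of safety and feasibility. It has no hypothesis or comparator, and descriptive analysis suits that design. Any reader given 0/30 or 29/30 can compute the interval, so nothing is lost or biased. That is largely fair, and it is why no test, performance goal or larger sample is asked for. It does not answer the whole point. Sections 6, 8.1 and 11.2 speak of safety and effectiveness rather than feasibility alone, and the sponsor's own summary would still omit the uncertainty. Readers also need a settled denominator to do the calculation.

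Four stronger readings might be inferred, and the documents do not support them:
- *That 30 is too few, or was chosen without any rationale.* Section 11.2 does give a rationale, the earlier trial. Its figures are not supplied, and no target rate exists against which 30 could be judged inadequate.
- *That the plan rules out intervals.* Section 11.1 leaves the choice of descriptive statistics open. It neither promises nor excludes intervals.
- *That the effectiveness result rests on complete cases.* Section 11.6 is confined to safety, and feasibility is recorded during the operation.
- *That no analysis population is named.* Sections 7 and 8.2 name one. The gaps are attempted use, the undefined safety population and the removal rule in 11.6.

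The sentence in 11.1 on describing missing endpoint data helps, but it does not tie the missing number to each proportion.

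**Conclusion.** The point stands as a gap between claim and planned output, and the change should be made. Section 11.2 asserts adequate evidence without a rate or precision, and no interval is planned for any proportion. At the maximum of 30 subjects, the best possible result still leaves a true event rate up to 11.6% and a true success rate down to 88.4% compatible with the data; fewer subjects widen both. These figures rest on an assumed exact two-sided 95% level. At 90% and 99% the zero-event limit runs from 9.5% to 16.2%. The denominator concern is real for safety and for attempted use. It does not extend to loss of feasibility results through follow-up.

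**What to change.** **(a) Sections 11.1 and 11.4.**
- Report exact (Clopper-Pearson) two-sided 95% intervals for the feasibility proportion and for the proportions of subjects with serious, device-related and procedure-related events.
- Use as denominator all subjects in whom the device was used or attempted. Keep those with incomplete safety follow-up in it, aligning 11.6 and the safety population in 11.4 accordingly, and show the number with missing data beside each proportion.
- Reconcile this denominator with the exclusion in 9.1.2 for abnormality found after surgery has begun. List those subjects separately, and state how a subject is counted when the device was attempted before another retractor was used, given the definition in 7.2.

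**(b) Section 11.2.** Replace the sufficiency statement with the precision obtained at 30 subjects and at smaller numbers, using the values for 30, 25 and 20 above. Word the claim, and the overall summary in 11.1, as preliminary evidence bounded by those intervals. The objective in section 6 can stay as it is.

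**Cost.** A protocol amendment under 15.5, approved by all parties who approved the protocol; a feasibility table and a few added rows and columns; and a more modest stated claim. No extra subjects or visits, no hypothesis test and no performance goal.
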